## 5.3 Future Directions

If feasibility is achieved on this study, then future plans would include analysis of secondary and exploratory objectives to determine if there are any trends towards a clinically-meaningful and plausible study endpoint, which would be further developed in a larger Phase II study. We have several key palliative care oncology collaborators, and ultimately plan to propose the Phase II concept through a cooperative group such as the [Palliative Care Research Cooperative Group](#) or the [Alliance in Clinical Oncology Trials](#) Symptom Intervention Committee, both of which [name] is an active member.

## 5.4 Other Therapy

Akynzeo® should be used with caution in patients receiving concomitant medications that are primarily metabolized through CYP3A4. The plasma concentrations of CYP3A4 substrates can increase when co-administered with AKYNZEO. The inhibitory effect on CYP3A4 can last for multiple days.

Length of washout period will be one week prior to Day 1 and/or 5 half-lives whichever is longer for any drug that is a known strong CYP3A4 inducer and/or strong or moderate CYP3A4 inhibitor. A list of known *in vivo* strong CYP3A4 inducers and inhibitors is available from the U.S. Food and Drug Administration. Strong CYP3A4 inducers include, but are not limited to, rifampin, St. John's wort, phenytoin, and efavirenz. Strong CYP3A4 inhibitors include, but are not limited to, ketoconazole, grapefruit juice, clarithromycin, and erythromycin. Use of any drug that is a known weak CYP3A4 inhibitor and/or a known CYP3A4 substrate is permitted. See Appendix 2 for a more comprehensive list of strong and moderate CYP3A4 inhibitors and strong CYP3A4 inducers.

Standard of care for routine CINV prophylaxis at the UCSD Moores Cancer Center follows NCCN guidelines. Routine CINV prophylaxis may be administered concomitantly throughout the 1-week treatment and follow-up period of this study. Patients receiving HEC are pretreated with a three-drug regimen, including an NK1 antagonist, 5-HT3 receptor antagonist, and glucocorticoid. Patients receiving MEC receive a 5-HT3 receptor antagonist and a glucocorticoid. Lastly, patients receiving low emetogenic chemotherapy do not receive any standard CINV prophylaxis. For all types of chemotherapy, use of routine breakthrough medication at UCSD, which includes a dopamine antagonist (i.e. prochlorperazine) and/or a benzodiazepine (i.e. lorazepam) will be permitted.

Unless there is a need for urgent intervention, additional medication for refractory CINV will be prohibited. This includes over-the-counter medications, medical marijuana, herbal supplements, and investigational agents for CINV. Other medications, which are considered necessary for the patient's safety and wellbeing, may be given at the discretion of the investigator.

## **5.5 Efficacy Measures:**

### **5.5.1 Patient Medication Diary**

Subjects will be asked to record all oral and self-administered medications received while on study. This will include any rescue medications used to treat their CINV each day, as well as any vitamins, homeopathic/herbal remedies, nutritional supplements, over-the-counter analgesic medication use, and all other over-the-counter "as needed" medications. Subjects will complete this diary (Appendix 3) on the day of Akynzeo® treatment (Study Day 1) and daily during the post-treatment observation portion of the study (Study Days 2-7).

### **5.5.2 Multinational Association of Supportive Care in Cancer (MASCC) Antiemesis Tool® (MAT)**

The MAT is a validated tool to measure CINV in 24-hour intervals developed by members of Multinational Association for Supportive Care in Cancer (MASCC) to assist patients and oncology professionals in communicating accurately about the prevention and control of nausea and vomiting that may occur with chemotherapy. The concept of the MAT is to provide an easy-to-use and easy-to-evaluate tool to assist in providing the best individual care to patients. Additionally, the tool will aid treatment centers in understanding the effectiveness of their antiemetic strategies. The MAT was first created and posted in 2004. It is now available in eleven languages, obtained by the standard forward/backward translation process. The MAT consists of eight items. Four of these items refer to the occurrence, duration, and frequency of acute nausea and vomiting, and four refer to the occurrence, duration, and frequency of delayed

nausea and vomiting. Dichotomous items are scored “0” (“No”) or “1” (“Yes”) and continuous variables as marked on the 0-10 scale. In total, there are 4 dichotomous variable items and 4 continuous variable items. There is no summing of items; instead, items are evaluated on their own in clinical practice. Each subject will complete a written form of the MAT at approximately the same time each day during the study. The MAT will be completed daily for 4 days after CINV prophylaxis and after Akynzeo® treatment (Study Day 1). Thereafter, it will be completed daily during the post-treatment observation portion of the study at the same time each day starting 24 hours from the time of previous questionnaire completion. English and Spanish versions of the MAT will be made available at study activation. Additional foreign translations will be performed as needed.

### **5.5.3 Functional Living Index Emesis (FLIE) Scale**

The FLIE is a validated patient-reported measure of the impact of CINV on daily life, which measures a 5-day recall. The FLIE is a short, self-administered instrument containing two domains, one for nausea (nine items) and one for vomiting (nine items). Responses to each question are rated on a 100mm visual analog scale that is scored on a one to seven-point scale as described in the FLIE scoring manual. A higher score indicates a better quality of life. Minimal or no impact of CINV on daily life will be defined as an average score of more than six on the seven-point scale (i.e. 108 total score or greater than 54 domain score). The FLIE will be completed on the 5th day after CINV prophylaxis, and on the day of Akynzeo® treatment (Study Day 1). During the post-treatment observation portion of the study, the FLIE will be completed on Day 5 only. English and Spanish versions of the MAT will be made available at study activation. Additional foreign translations will be performed as needed.

### **5.5.4 Healthcare Utilization**

CINV healthcare utilization data including information on the number and location of any emergency room visits, hospitalizations, and infusion center visits will be obtained via phone interview assessment on a daily basis over the seven-day treatment and follow-up periods. Phone calls will reference time since last phone interview and review prior responses. Study subjects will be asked to report all symptoms and problems leading up to the health care contact. All non-UCSD emergency room visits, hospitalizations, or infusion center visits will be followed-up with a medical request to verify the symptoms and reasons for such contacts. Records will be reviewed by study staff, and PI will be consulted for any clarifications. The primary and multiple secondary reasons for emergency room visits, hospitalizations, or infusion center visits will be recorded.

### **5.5.5 Patient Preference**

On Study Day 7, subjects will be asked to complete a five-point Likert scale containing the question “On a scale of 1-5, how likely are you to ask your doctor for Akynzeo® to treat your refractory CINV in the future?” Questionnaire results will be used to determine patient preference for future use of Akynzeo® for refractory CINV.

## **6.0 Study Drug Regimens**

---

Study drug (Akynzeo®) is an oral fixed-dose combination of 300 mg of netupitant and 0.5 mg of palonosetron. Akynzeo® will be administered once as an oral capsule and will be supplied as 300 mg netupitant/0.5 mg palonosetron hard gelatin capsules with a white body and caramel

---

cap with "HE1" printed on the body. All study drug will be supplied by Helsinn, using the current marketed product. IDS will label the study drug with the drug name, study reference number and storage conditions. Study drug will be dispensed to the subject by UCSD Investigational Drug Services (IDS). IDS will be responsible for all study drug shipments and accountability. After refractory CINV is confirmed and all study-related procedures completed on Day 1, subjects will be instructed to take one Akynzeo® capsule. Subjects will be administered a single, oral fixed-dose combination of 300 mg of netupitant and 0.5 mg of palonosetron. Akynzeo® must be kept in a secure place under appropriate storage conditions, as specified on the label and in the Investigator's Brochure. All study drug will be stored in original containers until dispensed to the study patients.

If a patient vomits after taking their Akynzeo® dose within 12 hours and the capsule is expelled from the body intact, it will be considered a missed dose. The patient will be instructed to take a picture of the capsule (if possible) and contact the PI who will determine if the patient should repeat up to one additional dose of Akynzeo®. Any changes from the dosing schedule including missed doses should be recorded in a CRF.

### **6.1 Study Drug Requested Per Patient**

1 capsule (300 mg of netupitant and 0.5 mg of palonosetron) per patient

### **7.0 Safety Measures**

---

A physical examination and complete metabolic profile will be assessed at screening to evaluate for the presence of any pre-treatment abnormalities and to confirm eligibility. Physical examination and laboratory testing to evaluate adverse effects that develop during the seven-day treatment and follow-up periods will be performed according to routine frequency for monitoring of the subject's cancer according to the treating oncologist.

Subjects will also be monitored for evidence of QTc interval changes at screening (an EKG will be required prior to Akynzeo® treatment on C2D1) and during the study treatment period on Study Day 3±3 days with a single EKG. If the patient experiences any worsening cardiac symptoms, including, but not limited to dizziness, shortness of breath, or chest pain, during the study period, additional EKG(s) will be performed as clinically indicated.

Daily safety assessments will be performed on the day of Akynzeo® treatment (Study Day 1), and daily during the post-treatment observation portion of the study (Study Days 2-7). All adverse events will be graded according to National Cancer Institute Common Terminology Criteria for Adverse Events (CTCAE) version 4.03.10

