**SCHEDULE OF EVENTS**

	Screening	Treatment (Study Day 1)	Follow-Up (Study Day 2-3) 	Follow-Up (Study Day 4-7) 
Informed consent	X			
Inclusion/exclusion criteria	X			
Demographics	X			
Medical and surgical history	X			
ECOG Performance Status	X			
Confirmed presence of refractory CINV	X			
Serum pregnancy test 	X			
Physical exam with vitals, weight 	X		per routine frequency	
Complete metabolic profile 	X		per routine frequency	
Complete blood count with differential, platelets 			per routine frequency	
EKG QTc evaluation	X 		X 	
Patient CINV risk factors		X		X
Akynzeo® dispensing and administration		X		
Patient medication diary		X		
Collect hospitalization and emergency room visit data		X	X	X
Concomitant medications	X	X	X	X
Adverse event monitoring		X	X	X
MASCC Antiemesis Tool  (MAT)	X	X	X	X
Functional Living Index for Emesis (FLIE) scale 	X	X		X 
Patient preference Likert-scale				X 

 Women of childbearing potential only

 Subjects will be monitored for a total of 6 days following Akynzeo® dosing

 QTc evaluation on Day 3±3 days with single EKG. If patient experiences worsening cardiac symptoms during the study, additional EKG(s) will be performed as clinically indicated

 Complete on Day 5 only

 Daily unless otherwise indicated. Daily safety assessment and hospitalization/ER visit information on Days 2-7 may occur via in-person visit or telephone call from a study team member. Subjects will also receive a daily reminder (via in-person visit or telephone call) to complete required questionnaires/diaries.

 Complete on Day 7 only

 EKG, laboratory and physical exam results obtained within 4 weeks prior to the informed consent date may be used to fulfill study requirements. EKG results may be obtained after screening processes yield positive refractory CINV.

 To be completed daily for 4 days after CINV prophylaxis or Akynzeo® dosing.

 To be completed on the 5th day after CINV prophylaxis or Akynzeo® dosing

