#### **3.1 Inclusion Criteria**

1. Adults greater than or equal to 18 years old.
2. Must have a histologically confirmed cancer diagnosis.
3. Must have refractory CINV defined as nausea and/or vomiting that occurs after the first cycle of cancer targeted therapy despite guideline-based prophylaxis and after first-line rescue medication with either a dopamine receptor antagonist, steroid, and/or benzodiazepine.
4. Eastern Cooperative Oncology Group (ECOG) performance status less than or equal to 2.
5. Life expectancy greater than 3 months.
6. Corrected serum calcium level less than or equal to 10.5 mg/dL.
7. Women of child-bearing potential must agree to use adequate contraception (hormonal or barrier method of birth control; abstinence) prior to study entry, for the duration of study participation, and for 14 days following completion of therapy.  
A woman of child-bearing potential is any female (regardless of sexual orientation, having undergone a tubal ligation, or remaining celibate by choice) who meets the following criteria:
  - a. Has not undergone a hysterectomy or bilateral oophorectomy; or
  - b. Has not been naturally postmenopausal for at least 12 consecutive months (i.e., has not had menses at any time in the preceding 12 consecutive months)
8. Women of child-bearing potential must have a negative pregnancy test prior to initiating study treatment.
9. Ability to understand and willingness to sign a written informed consent.

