## **5.0 Description of Procedures**

---

Eligible subjects will be identified in weekly palliative care patient triage meetings. Patients who are 18 years of age or older, have histologically confirmed cancer, and confirmed refractory CINV will be eligible.

After obtaining written informed consent and verifying that the study subject meets all eligibility criteria, the subject will be enrolled in the study through the UCSD Moores Cancer Center Clinical Trials Office. The study coordinator will educate the subject on how to complete the MASCC Antiemesis Tool (MAT), and FLIE scale after CINV prophylaxis. Subjects will be asked to complete the MAT on a daily basis for 4 days and then the FLIE on the 5th day after cancer treatment. Subjects will be allowed to participate only once in the study. Study Day 1 will be the day of Akynzeo® dosing. Subjects will receive a single capsule of Akynzeo® (300 mg of netupitant and 0.5 mg of palonosetron) on Study 1. Study drug may be taken with or without food. Subjects will complete a study drug diary to document date and time of Akynzeo® administration. On Study Day 1, the study coordinator will educate the subject on how to complete the written MASCC Antiemesis Tool, and FLIE scale, and medication diary for each day following the Study Day 1. An adequate number of copies of each subject questionnaire and diary will be provided to the subject on Study Day 1 for completion at home during the post-treatment observation portion of the study (Study Days 2-7) as needed.

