### **5.1 Patient CINV Risk Factors**

Classifying CINV risk by chemotherapy type has provided a valuable framework for the development of international prophylactic antiemetic guidelines. However, considerable work has revealed a number of patient specific variables that may contribute to emetic risk. Therefore, antiemetic guidelines relying solely on emetogenicity of chemotherapy may potentially undertreat patients at higher individual emetic risk than what the chemotherapy alone suggests. CINV patient-related risk prediction models have been developed. Based on data from these models, several key patient risk factors will be collected on Study Day 1 prior to Akynzeo® dosing including: age, sex, alcohol consumption, history and severity of previous CINV, history of morning sickness with pregnancy, history of motion sickness, less sleep the night before chemotherapy, and pre-chemotherapy anxiety.

During the post-treatment observation portion of the study, subjects will receive a daily phone call from a member of the study team to inquire about any adverse event that the subject may

be experiencing and whether they have had any hospitalizations or emergency room visits since the last contact. During these calls, the study team member will also remind the subject to complete the MASCC Antiemesis Tool and medication diary. On Study Day 5 only, the subject will also be instructed to complete the FLIE scale. The subject will be asked to return to clinic on Study Day 3 (+3 days) for a single EKG. Additional clinic visits, physical exams, or laboratory tests performed during the 7-day treatment and follow-up periods will be scheduled according to routine care and according to the subject's treating physician.

Subjects will be asked to return all completed and unused study materials, including subject diaries and questionnaires to a member of the study team at their next routine clinic visit.

A more detailed description of selected assessments is included in the Efficacy Measures and Safety Measures sections.

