#### Information about this brief form:

The MASCC Antiemesis Tool (MAT) is a way to help your doctors and nurses be sure you get the best care there is to prevent nausea and vomiting from chemotherapy. By filling out this form, you can help us make sure that you are having the best control of these possible side effects. Here are the definitions used on this form:

**Vomiting:** The bringing up of stomach contents.

**Nausea:** The feeling that you might vomit.

Please answer all questions. There are no right or wrong answers, only your impression. If you have any concerns about how or when to complete this form, please ask!

Please notice that Question #4 and Question #8 have a different style. These questions are scales. For this type of question, just circle the number from 0 to 10 that most closely resembles your experience with your nausea and vomiting and write the number in the box to the right. An example of this form of question (but dealing with parking) is given below. Feel free to practice with this example or ask one of us to go over it with you.

How much difficulty did you have parking your car today?

0	1	2	3	4	5	6	7	8	9	10
None										
As much as possible										

(Write the number in this box)

Please return the form shortly after completing it, as discussed with us. Thank you!

MASCC Antiemesis Tool

Please fill this out the day after chemotherapy on:

Day  Month  Day of the Week

**Nausea and Vomiting  
during the first 24 hours after chemotherapy:**

(This page refers to the first 24 hours following chemotherapy):

1) In the 24 hours since chemotherapy, did you have any vomiting? Yes  No   
(Select one)

2) If you vomited in the 24 hours since chemotherapy, how many times did it happen?   
(Write the number of times in this box)

3) In the 24 hours since chemotherapy, did you have any nausea? Yes  No   
(Select one)

4) If you had nausea, please circle or enter the number that most closely resembles your experience.

How much nausea did you have in the last 24 hours?

0 1 2 3 4 5 6 7 8 9 10  
None As much as possible

(Write the number in this box)

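### The plan does not settle when the capsule is taken relative to chemotherapy, so the five-day complete-response window has no fixed position after chemotherapy and may not match the MAT emesis data

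*Combined protocol and SAP*

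**What the plan says.** All references are to the combined protocol and SAP.

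**When the capsule is taken**
- Section 7.0 (Safety Measures): "an EKG will be required prior to Akynzeo® treatment on C2D1". C2D1 appears nowhere else and is not in the list of abbreviations.
- Section 6.0 (Study Drug Regimens): "After refractory CINV is confirmed and all study-related procedures completed on Day 1, subjects will be instructed to take one Akynzeo® capsule". No cycle or chemotherapy day is given.
- Section 5.0: "Study Day 1 will be the day of Akynzeo® dosing". Chemotherapy is not mentioned in that definition.
- Section 3.1, item 3: eligibility rests on "nausea and/or vomiting that occurs after the first cycle of cancer targeted therapy despite guideline-based prophylaxis and after first-line rescue medication". It is not limited to cycle 2.
- Schedule of Events: "Confirmed presence of refractory CINV" is a screening item, and footnote 7 adds "EKG results may be obtained after screening processes yield positive refractory CINV".
- Section 5.1: the risk factors collected on Study Day 1 before dosing include "less sleep the night before chemotherapy, and pre-chemotherapy anxiety".
- Section 5.4: routine prophylaxis is allowed during the study week, so chemotherapy may fall within it.

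**When outcomes are measured**
- Section 2.2: complete response means no emesis and no rescue for five days from the capsule. Section 9.3 repeats the endpoint without the five days.
- Schedule of Events, footnote 8: the MAT is completed daily for four days, counted from prophylaxis or from the capsule. Section 5.5.2 continues it daily through post-treatment observation.
- Appendix 1: the MAT items are worded from chemotherapy, for example "In the 24 hours since chemotherapy, did you have any vomiting". The second page covers the time after the first 24 hours, up to four days after chemotherapy.

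**The concern.** The title and objectives describe treating refractory CINV. Section 7.0, the pre-chemotherapy risk items and the MAT wording suggest a dose given with a cycle of chemotherapy. No passage states the interval between chemotherapy and capsule. Two coordinators could follow the text faithfully and dose at different points.

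The same five days then measure different things. With the capsule on the day of chemotherapy, they span the acute phase (under 24 hours, Section 1.1) and the delayed phase, as a prevention endpoint does. With the capsule some days later, they measure control of symptoms after the acute phase has passed. One pooled proportion would not say which question it answers. Section 5.3 intends to look through the secondary results for a plausible endpoint for a further study, so a reader of that proportion needs to know.

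There is also a data problem. The endpoint runs from the capsule, but the main dated record of emesis asks about time since chemotherapy.

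**Working it through.** **1. The plan's own design figure.** Section 9.2 gives n = 50, 70% against 85%, Type I error 0.05 and 80% power, without stating sidedness. For a one-sample z test,

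power = Φ{[(p1 − p0)√n − z·√(p0(1 − p0))] / √(p1(1 − p1))}.

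- One-sided: (0.15 × 7.071 − 1.645 × 0.4583) / 0.3571 = 0.859, so power is 80.5%. The plan's figure is reproduced.
- Two-sided: (1.0607 − 1.960 × 0.4583) / 0.3571 = 0.455, so power is 67.5%.

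Dosing time does not enter this calculation. The primary endpoint is completion of procedures.

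**2. Can the timing passages be read together?** Yes, in one way. Refractory CINV is confirmed at screening after cycle 1, the EKG follows, and the capsule is given on C2D1. This satisfies the Schedule of Events and Sections 5.0, 6.0 and 7.0. It cannot serve a patient who first qualifies in cycle 2 or later, because C2D1 has then passed; Section 3.1 does not exclude such a patient. The reading is possible but is not stated and does not cover everyone eligible.

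**3. Position of the response window.** Let d be the days from chemotherapy to capsule. The documents give no value, so d = 0 to 4 is an assumption. The window is day d to day d + 5 after chemotherapy, and its overlap with the first five post-chemotherapy days is 5 − d.

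**4. Coverage by the MAT as printed.** Reading the form's four days as 96 hours, its two pages cover 0 to 96 hours after chemotherapy. The response window is 24d to 24d + 120 hours. The part covered is 96 − 24d hours.

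| d (assumed) | Response window, days after chemotherapy | Overlap with first 5 days | Hours of the 120 covered by the printed MAT |
|---|---|---|---|
| 0 | 0–5 | 5 days (120 h) | 96 |
| 1 | 1–6 | 4 days (96 h) | 72 |
| 2 | 2–7 | 3 days (72 h) | 48 |
| 3 | 3–8 | 2 days (48 h) | 24 |
| 4 | 4–9 | 1 day (24 h) | 0 |

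The acute phase lies inside the window only at d = 0. Even there, the printed form stops 24 hours before the window ends. Four daily forms counted from the capsule (footnote 8) would also fall one day short of five. The daily completion in Section 5.5.2 would supply enough forms, but each would still ask about time since chemotherapy, and the delayed items ask about one multi-day period rather than one day.

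**The case against.** **What stands.**
- The passages are not strictly contradictory, as step 2 shows. Section 6.0 does not say that the patient is symptomatic at dosing. The fair description is an unresolved ambiguity.
- The response window has a fixed start and length. A reader might infer that it has no meaning at all; Section 2.2 does not support that. Only its position relative to chemotherapy is open.
- The sleep and anxiety items are weak evidence for dosing on the day of chemotherapy. The Schedule of Events repeats the risk-factor assessment in the Day 4–7 column, so they can be answered in retrospect.
- Some of the needed data are already captured. Section 5.0 has a drug diary with capsule date and time, and Appendix 1 has a chemotherapy date field. Section 5.5.1 has a daily medication diary through Day 7 for rescue use. The FLIE items recall the last five days and are completed on Study Day 5, which broadly fits the response window. The daily calls ask about adverse events and may pick up vomiting.

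**Stronger readings that the documents do not support.**
- That the overlap is only one day in five. That is the far end of an assumed range; at d = 0 the overlap is complete.
- That later windows cover waning symptoms. No passage gives the time course in these patients.
- That early emesis unfairly counts as failure before peak concentration. Section 1.3 gives about 5 hours, in healthy subjects. That is 5 of 120 hours, and it would apply whatever the dosing day.
- That the 90% benchmark in Section 9.3 fails because of dosing time. Reference 17 is a prevention trial, so its fit to a refractory population is open to question at any dosing time. That is a separate point.
- That the result cannot guide the next study. Section 5.3 asks only for trends, and only if feasibility is achieved.

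None of this supplies the missing statement of how Study Day 1 relates to chemotherapy, or makes the MAT wording match the endpoint.

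**Conclusion.** The concern holds as an unsettled design element affecting a secondary endpoint. The text leaves the chemotherapy-to-capsule interval open, so the five-day window could share anything from all five to one of the first five post-chemotherapy days if d runs from 0 to 4. That range is assumed, and the actual spread may be narrower. A pooled complete-response rate may therefore mix prevention-type and treatment-type responses.

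The mismatch with the MAT depends less on that assumption: as printed, the form covers at most 96 of the 120 hours at any d in the range. The effect on the observed response rate cannot be sized from the documents. The primary completion endpoint and the sample size of 50 do not change. The correction should be made because it is cheap and the secondary results are meant to inform the next study.

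**What to change.** 1. **Reconcile the timing text.** The sponsor and investigator should bring the Schedule of Events and Sections 3.1, 5.0, 5.1, 5.5.2, 6.0 and 7.0 to one statement of how Study Day 1 relates to chemotherapy, and define or remove C2D1. Which timing is right is a clinical decision, on which this review takes no view.
2. **Align the emesis data with the endpoint.** Anchor the recall wording and completion days of the post-dose MAT to the same event and the same five-day period as complete response, and restore the five days in Section 9.3. Section 2.2 already calls the tool modified, so state the change in wording.
3. **Use the dates already collected.** Carry the chemotherapy date (Appendix 1) and the capsule date and time (Section 5.0 diary) into the case report form, and report the interval descriptively. Show complete response by interval only if the reconciled text still lets the interval vary; with 50 subjects such a split is descriptive.

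The cost is protocol wording, a revised post-dose MAT page, case report form entries for data already requested, and one descriptive table. No extra subjects or visits are needed.
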